#### **7.4 Inclusion of Women and Minorities**

Adult men and women of all races and ethnic groups are eligible for this trial.

## 8 STUDY TREATMENTS

### 8.1 Description of Study Medications

#### 8.1.1 Brequinar

Brequinar will be supplied as 100 mg capsules. Dosing will be a single 5-day course of brequinar 100 mg once daily for 5 doses. The initial brequinar dose (Day 1) should be administered as soon as possible based on study drug availability from the investigational pharmacy. At least the first dose of study medication is to be taken in the hospital. Subjects in the brequinar group discharged before Day 5 will be dispensed brequinar to take at home daily until all 5 doses have been taken.

### 8.2 Treatment Administration

This will be a phase 1a randomized, open label, multi-center study with approximately 24 subjects. All subjects will receive standard of care (SOC) per institutional guidelines for SARS-CoV-2 infection. Subjects will be randomly assigned in a 1:2 ratio to standard of care alone or standard of care plus brequinar. The brequinar dosing interval should be  $24\text{h} \pm 6\text{h}$ . If discharged prior to Day 5, the subject may take any remaining doses once a day at home. In this case, the subject is to record dosing using a medication diary provided by the study team. The diary information will be provided to the study team either verbally or electronically or during an in-person visit.

#### 8.2.1 Safety/Tolerability

Safety/tolerability is assessed for each subject at each study visit using the Common Terminology Criteria for Adverse Events v4.03 (CTCAE).

Adverse events (AEs) commonly observed in patients treated with brequinar are provided in the Investigator's Brochure (IB) and include thrombocytopenia, nausea, anemia, diarrhea, vomiting, leukopenia, stomatitis, rash, granulocytopenia, fatigue, and infection. In a study of 209 subjects treated once-weekly (DuP 785-012, see Brequinar IB [5]), the deaths of three patients were attributed to study drug toxicity (two to hemorrhage, one following acute renal failure). Severe toxicities grades (Grades 3 to 4) which typically led to discontinuation in this study included hematologic toxicities (anemia, thrombocytopenia, leukopenia, granulocytopenia), digestive system toxicity (nausea, vomiting, stomatitis, others including gastric hemorrhage) and mucositis.

In three oncology studies (Study 785-001 [16], 785-003 [17], and 785-005 [18]) with five consecutive days of intravenous (IV) brequinar dosing and 168 subjects, there were no toxic deaths. For subjects from these three studies who were treated with a dose of 100 mg or below (as will be dosed in CCB-CRISIS-01), AEs through 21 days showed that 2 of 39 subjects (5.1%) had a severe (Grades 3 or 4) AE related to study drug (1 subject each with hyperbilirubinemia and hyperglycemia), and no subjects discontinued from the study due to a study drug-related AE. The few study drug related AEs through 21 days at or below the 100 mg dose from these three studies included 2 subjects each with nausea, vomiting, and creatinine elevated and one subject each with thrombocytopenia and diarrhea. When only studies with oral dosing were considered at this dose level (Studies 785-022 [19], 785-031 [20], and 785-034 [21]), the study drug related AEs through 21 days (each observed in one subject only) included diarrhea, headache, nausea,

PROTOCOL NUMBER: CCB-CRISIS-01  
PROTOCOL VERSION FINAL DATE: 10SEPT2020

Page 29 of 58

pruritus, abdominal pain, anorexia, chest pain, dry mouth, fatigue, keratosis, stomatitis, and vomiting. See brequinar IB (5).

In most instances, brequinar-related toxicities were transient, clinically manageable and reversible upon discontinuation of brequinar treatment. Any of these events reported with brequinar use can be serious in nature and may result in death.

A 5-day course of oral brequinar administered once daily at a low level relative to those administered in the cancer studies is expected to be safe and well tolerated in the COVID-19 population.

### 8.3 Study Discontinuation

Subjects will remain in the study through at least Study Day 15 (or longer if needed to follow up study drug-related adverse events). Mortality is assessed via a phone call or other digital media at Day 29.

After treatment, participants will be monitored through at least Study Day 15 (or longer if needed to follow study drug-related AEs/SAEs). Participants may discontinue from the study by withdrawing consent at any time or for any reason as presented in [Section 9.7](#).

### 8.4 Stopping Criteria

#### 8.4.1 Individual Stopping Criteria

- Participants who develop a Grade 3 symptomatic toxicity that is assessed by the investigator to be related to the study drug are to be permanently discontinued from study treatment.
- Participants who develop a Grade 4 symptomatic toxicity, regardless of relatedness to study drug, are to be permanently discontinued from study treatment.
- Subjects who develop Grade 3 or 4 toxicities are to be followed by re-evaluation every 2 days, as feasible, until the toxicity returns to  $\leq$  Grade 2 severity.

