## 2 SYNOPSIS

CCB-CRISIS-01 SYNOPSIS	
IND	149291
Title	The CRISIS Study: A randomized open-label study assessing the safety and anti-coronavirus response of suppression of host nucleotide synthesis in hospitalized adults with coronavirus-19 (COVID-19)
Protocol	CCB-CRISIS-01
Rationale	
Brequinar is a potent DHODH inhibitor that has been studied in more than 1,000 cancer, psoriasis, and organ transplant patients. DHODH inhibition has been extensively studied as a potential therapeutic target in the treatment of RNA-based viruses. The inhibition of DHODH is effective in inhibiting viral replication in pre-clinical models involving many RNA-based viruses with nanomolar potency and a high selectivity index. In these pre-clinical models, the benefit of DHODH inhibition can be reversed by the supplementation of exogenous nucleotides, confirming that the on-target effect of host pyrimidine depletion is key to the anti-viral activity. The primary dose-limiting adverse effects have included thrombocytopenia and mucositis.
 
The CRISIS trial will study standard of care (SOC) and SOC with 5 days of DHODH inhibition. Clear Creek Bio hypothesizes that a defined 5-day course of brequinar will inhibit the enzyme DHODH to a degree sufficient to result in the transient depletion of host pyrimidine nucleotides, thereby inhibiting viral replication. A recent publication demonstrated that inhibitors of DHODH could potentiate the activity of inhibitors of RNA-dependent RNA polymerase (RdRp) in the treatment of dengue virus, another single-stranded RNA virus similar to SARS-CoV-2. This inhibition of viral replication may restore the balance in favor of the host immune system for the clearance of SARS-CoV-2.
 
Marketed DHODHi medications are available, including leflunomide or teriflunomide, however these are very weak inhibitors of DHODH with cellular potency ~500 times lower than brequinar. These low potency inhibitors of DHODH are not expected to have the ability to acutely lower the pool of intracellular pyrimidines to the degree that is required for decreasing the viral load associated with SARS-CoV-2 infection, making brequinar the better choice for acute SARS-CoV-2 infection. Brequinar has not been previously tested as an anti-viral.

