	
 
5. Platelets <math>\leq 150,000</math> cell/mm^3.
 
6. Hemoglobin < 10 gm/dL
 
7. Absolute neutrophil count < 1500 cells/mm^3
 
8. Renal dysfunction, i.e., creatinine clearance < 30 mL/min
 
9. AST and/or ALT > 1.5 ULN, or total bilirubin > ULN
 
10. History of bleeding disorders or recent surgery in the six weeks preceding enrollment
 
11. Concomitant use of agents known to cause bone marrow suppression leading to thrombocytopenia
 
12. History of gastrointestinal ulcer, or history of gastrointestinal bleeding.
 
13. History of hepatitis B and/or C infection, active liver disease and/or cirrhosis.
 
14. Heart failure, current uncontrolled cardiovascular disease, including unstable angina, uncontrolled arrhythmias, major adverse cardiac event within 6 months (e.g. stroke, myocardial infarction, hospitalization due to heart failure, or revascularization procedure).
 
15. Life expectancy of < 5 days in the judgment of the treating clinician.
 
16. Evidence of critical illness defined by at least one of the following:             
 
a. Respiratory failure requiring at least one of the following:                 
 
i. Endotracheal intubation and mechanical ventilation, noninvasive positive pressure ventilation, ECMO, or clinical diagnosis of respiratory failure (i.e., clinical need for one of the preceding therapies, but preceding therapies may not be able to be administered in setting of resource limitation)
 
ii. Shock (defined by systolic blood pressure < 90 mm Hg, or diastolic blood pressure < 60 mm Hg or requiring vasopressors)
 
 
 
b. Multi-organ dysfunction/failure.
 
 
 

Treatment
	
All subjects will receive standard of care (SOC) per institutional guidelines. Subjects will be randomly assigned to SOC alone or SOC plus brequinar 100 mg daily x 5 days.

Stopping Criteria
	
Individual Criteria:
 
 
• Participants who develop a Grade 3 symptomatic toxicity that is assessed by the investigator to be related to the study drug are to be permanently discontinued from study treatment.
 

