#### **Subjects in the Brequinar Treatment Group**

If the subject is in the brequinar treatment group and is being discharged prior to completing the study, ensure a hematology/chemistry sample is obtained prior to discharge on the day of discharge. The subject is to return to the research or out-patient facility for the Days 7 and 15 visits if able and permitted. If unable or not permitted to return to the research facility due to COVID-19 restrictions, the remaining visit activities except for the lab draw will be conducted by phone

PROTOCOL NUMBER: CCB-CRISIS-01  
PROTOCOL VERSION FINAL DATE: 10SEPT2020

Page 22 of 58

or other digital media. The lab draw will be performed by an outpatient laboratory at a designated facility. Lab draws for any outpatient visits for the Day 7 and 15 visits are limited to safety labs (hematology and chemistry). Additional outpatient laboratory or study visits are to be conducted as needed for follow up of adverse events including hematologic toxicities.

PROTOCOL NUMBER: CCB-CRISIS-01  
PROTOCOL VERSION FINAL DATE: 10SEPT2020

Page 23 of 58

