#### 8.4.2 Study-Level Stopping Criteria

Following assessment by the Data Safety Monitoring Board (DSMB, see [Section 10.9](#)), the study is to be stopped as shown below:

- If  $\geq 4$  subjects on the brequinar treatment arm develop the same Grade 3 or 4 adverse event or symptomatic laboratory abnormality
- If  $\geq 8$  subjects on the brequinar treatment arm develop any Grade 3 or 4 adverse event or symptomatic laboratory abnormality.

### 8.5 Hospital Discharge Prior to Study Day 15

Subjects discharged from the hospital prior to the Day 15 visit are to return to a research facility when feasible for the remaining study visits. All scheduled study assessments are to be completed at these visits when conducted at a research facility.

PROTOCOL NUMBER: CCB-CRISIS-01  
PROTOCOL VERSION FINAL DATE: 10SEPT2020

Page 30 of 58

For subjects in the brequinar treatment group discharged from the hospital prior to Day 5, the subject is to take home the remaining doses of brequinar for daily self-administration. All subjects (brequinar and SOC) should have the scheduled assessments, e.g. lab samples and the nasopharyngeal swab, on the day of discharge and enter these results on the appropriate EDC page. Following discharge, subjects are to return to the research or out-patient lab collection facility for the remaining study visits, if feasible. Out-patient lab results are to be entered into the EDC and reviewed by a member of the study team. It is important that every effort be made to have subjects return at least on Days 7 and 15, if feasible. Subjects in the brequinar group are to record brequinar dosing on the medication diary provided by the study team. The study team will arrange for the subject to return any unused study medication to the research facility.

For all subjects, if discharge occurs on Days 10, 11, or 12, ensure a hematology/chemistry sample has been obtained on the day of discharge and record these results on the appropriate EDC page. Following discharge, the subject is to return to the research or out-patient lab collection facility for the Day 15 visit, if feasible. Out-patient lab results are to be entered into the EDC and reviewed by a member of the study team.

If discharge occurs on Days 13, 14 or 15, complete the Day 15 Final Visit activities prior to discharge. No further visits are required unless follow up is needed for a study drug-related AE or an SAE; the Day 29 mortality assessment is still to take place.

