### **10.8 Safety Monitoring for Hematologic Toxicities**

Myelosuppression is a known effect of DHODH inhibition that is associated with prolonged exposure and high doses. To reduce the risk of this effect with brequinar in COVID-19 subjects, the extensive brequinar safety database with over 1,000 patients has been evaluated to select a dose level expected to be safe and well tolerated with regard to hematologic toxicity. In addition to enhancing safety by selecting a relatively brief 5-day exposure and a low brequinar dose, all subjects in the clinical trial will initially be hospitalized as in-patients and will be under the care of highly qualified infectious disease, critical care, and associated medical personnel. As is standard of care for moderately to severely ill in-patients, daily samples will be obtained for hematology assessments including complete blood count with full differential (WBC, RBC, hemoglobin, hematocrit, platelet count, absolute neutrophils, absolute lymphocytes, absolute monocytes, absolute eosinophils, and absolute basophils). Any clinically significant out-of-range laboratory values will be assessed by hospital staff in a timely manner and treatment needs addressed as appropriate. Clinically significant out-of-range laboratory results will be reported as adverse events.

In addition to real time assessments by the treating clinical team, the Clear Creek Medical Monitor will assess the available hematology data on a weekly basis to identify any pathologic trends or safety issues. Any apparent increase in the expected rate or severity of hematologic safety events will be discussed with the Principal Investigators, the Sponsor, and the Medical Monitor. In addition, the Data Safety Monitoring Board will assess available hematology data on a periodic basis to independently assess any pathologic trends or safety issues. If the rate or severity of hematologic toxicities appears to be above the expected rate or the severity appears worse than that expected, the trial enrollment will be suspended and no further subjects will be treated while a comprehensive data review is conducted. Depending on the outcome of the safety review the study may be stopped, the design adjusted, or the study may continue as designed. Individual and study stopping rules are provided in [Section 8.4](#).

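### Section 8.4.1 requires stopping brequinar only for symptomatic toxicity, so the individual rule sets no count at which a silent severe thrombocytopenia or neutropenia ends dosing

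*Protocol*

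**What the plan says.** In the current version (10 September 2020), Section 8.4.1 has three bullets, repeated under Stopping Criteria in the Synopsis. Two stop the drug. At Grade 3 the stop applies to "Participants who develop a Grade 3 symptomatic toxicity that is assessed by the investigator to be related to the study drug". At Grade 4: "Participants who develop a Grade 4 symptomatic toxicity, regardless of relatedness to study drug, are to be permanently discontinued from study treatment". The third bullet drops the word *symptomatic*. It asks for every Grade 3 or 4 toxicity to be rechecked every second day where feasible until it falls to Grade 2 or below, and Section 10.1 repeats this. Neither place attaches a hold or a stop of dosing.

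The Synopsis rationale says: "The primary dose-limiting adverse effects have included thrombocytopenia and mucositis". Section 10.8 sets up monitoring for myelosuppression, under which "daily samples will be obtained for hematology assessments including complete blood count with full differential". For the action to take it refers back to Section 8.4: "Individual and study stopping rules are provided in" that section.

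On early discharge, Section 8.1.1 says that brequinar subjects "discharged before Day 5 will be dispensed brequinar to take at home daily until all 5 doses have been taken", and Section 8.5 says that "the subject is to take home the remaining doses of brequinar for daily self-administration". Section 8.2 and the footnote to the Appendix A schedule are permissive instead: there the subject *may* take, or be dispensed, the remaining doses. Section 3.9 tells sites to "ensure a hematology/chemistry sample is obtained prior to discharge on the day of discharge". No section makes dispensing depend on the result.

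**The concern.** The qualifier suits mucositis, which a patient feels. It does not suit thrombocytopenia or neutropenia, which can be severe on a blood count while the patient notices nothing. Section 10.8 collects the counts because myelosuppression is a known effect of this drug class, then points to an individual stopping rule in which no count, however low, stops the drug by itself.

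The entry criteria show that the sponsor regards these counts as relevant to safety: Section 7.3 excludes platelets at or below 150,000 and an absolute neutrophil count below 1500. There is no on-treatment counterpart. At stake is whether a subject with a silent but severe fall receives further doses, and whether up to eight sites would handle that subject alike. Safety is the primary objective, so how a hematologic toxicity is handled bears directly on what the trial is meant to show.

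**Working it through.** No figure in the plan needs reproducing. The check applies the rule case by case and then looks for any other text that would stop dosing.

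**Step 1. Section 8.4.1 applied to thrombocytopenia or neutropenia**

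| Case | Action required by 8.4.1 |
|---|---|
| Grade 3, related, symptomatic | Permanent stop |
| Grade 4, symptomatic, any cause | Permanent stop |
| Grade 3, related, no symptoms | Recheck every second day where feasible |
| Grade 4, no symptoms, any cause | Recheck every second day where feasible |

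The last two rows are the gap.

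**Step 2. Other text that could stop the drug**

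- Section 8.4.2 acts on the study, not on an individual's dosing.
- Section 9.7 requires withdrawal for a safety reason, a significant adverse event, or when the investigator or sponsor judges it best for the subject. It states no grade and no count, and it governs study participation. It also asks for all evaluations to be completed in subjects who leave before finishing treatment, unless consent is withdrawn, so follow-up need not be lost.
- Section 10 makes an asymptomatic laboratory value an adverse event if it is judged clinically significant or needs therapy. This opens the route to Section 9.7, again by judgment.
- Section 10.8 provides review by hospital staff, the investigator, the Medical Monitor and the DSMB, and possible suspension of enrollment. It gives no individual dosing threshold.

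No platelet or neutrophil limit for holding or stopping dosing appears in any of these.

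**Step 3. Take-home doses**

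Sections 8.1.1 and 8.5 read as instructions; Section 8.2 and Appendix A read as permission. A site can therefore decline to dispense, but nothing tells it when to. A subject discharged with a Grade 3 or 4 count would still be rechecked every second day where feasible (Sections 8.4.1 and 10.1). Section 3.9 adds extra outpatient laboratory visits as needed for hematologic toxicities.

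**Step 4. Size**

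Inputs are from Section 8.2.1 (39 subjects at or below 100 mg in three five-day intravenous oncology studies, adverse events through 21 days) and Section 3.6.2.

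- Related Grade 3 or 4 events: 2 of 39, one hyperbilirubinemia and one hyperglycemia. Related Grade 3 or 4 cytopenias: 2 − 1 − 1 = 0.
- Exact 95% upper limit for 0 of 39: 1 − 0.025^(1/39) = 0.0903, about 9.0%.
- Thrombocytopenia of any grade: 1 of 39 = 2.6%, described as mild.
- Doses that a stop can still prevent once the Day 1 dose is taken: 5 − 1 = 4 of 5.

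The 9.0% is not a rate for this rule. It covers 21 days, including the time after the last dose, and does not separate silent from symptomatic cases. The protocol gives neither the time to the lowest count nor the share without symptoms, so no expected number of affected subjects is calculated.

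**The case against.** The strongest reply is that Section 8.4.1 is not the whole protocol. Section 9.7 is worded as an obligation: once an event counts as a safety reason or as significant, withdrawal must follow. A clinically significant count is an adverse event without symptoms, and as a Grade 3 or 4 adverse event it also counts toward the study-level limits. A competent clinician seeing a Grade 4 platelet count would very probably stop the drug. This stands. A reader might infer that the protocol allows nothing beyond re-evaluation for a silent Grade 4 cytopenia. That is true of Section 8.4.1 alone and not of the protocol as a whole.

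A reader might also infer that the discharge-day count is the last one seen before the take-home doses, because Section 10.8 names Day 7 ± 2 as the next safety sample for subjects discharged early. For the subject in question this does not hold. A Grade 3 or 4 count at discharge triggers the recheck every second day and the additional outpatient tests, both outside the routine schedule.

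A third reply is that *symptomatic* stands in every protocol version shown, so it looks deliberate, and that adding only platelets and neutrophils is selective. Anemia is also a listed hematologic toxicity, and the two severe related events among the 39 were of bilirubin and glucose. It may well be deliberate, but no reason is given for applying the qualifier to a toxicity found by a count. The narrow scope is defensible: thrombocytopenia is the named dose-limiting laboratory effect, and Section 10.8 identifies myelosuppression as the known risk. The sponsor may choose to go wider.

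**Conclusion.** The point holds as a cheap improvement, not as a serious safety failure. The individual rule to which the hematologic monitoring section refers does not stop brequinar for an asymptomatic Grade 4, or related Grade 3, thrombocytopenia or neutropenia. Other sections can lead to a stop, and Section 9.7 compels one once its condition is met, but each depends on an undefined judgment. The documents do not support saying that such a subject would be left on the drug or unmonitored.

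The effect is probably very small: about 16 brequinar subjects, entry limits on both counts, at most four doses at issue, and no related severe cytopenia among 39 prior subjects. Those 39 were oncology patients dosed intravenously, and Section 3.6.2 says that no brequinar safety information exists in this disease, so the reassurance is limited. The conclusion assumes that the recheck bullet is not meant as an implied hold, which nothing in its wording suggests, and that a Grade 3 or 4 count can be recorded without symptoms, which the protocol's separate category of symptomatic laboratory abnormality implies.

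**What to change.** Add one bullet to Section 8.4.1 and to the Synopsis: *Grade 4 thrombocytopenia or neutropenia, regardless of symptoms or relatedness, and Grade 3 thrombocytopenia or neutropenia judged related to study drug, permanently stops brequinar. Take-home doses are withheld or stopped when the discharge-day count or a later count meets this criterion. The subject remains in study follow-up.*

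Other laboratory abnormalities can keep the present qualifier. For lymphopenia there is a specific reason: Appendix D lists a low admission lymphocyte count among the risk factors for COVID-19 progression, and Section 7.3 sets no lymphocyte limit at entry, so such values may reflect the disease.

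The change needs no new test or visit, because the counts are already collected. The downside is that a rare subject stops a five-dose course early.
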